9.6 Primary study parameter(s)

Data will be analyzed on an intention-to-treat basis. In addition, a per-protocol analysis will be performed.

The first primary outcome is postoperative complications, as scored by the Comprehensive Complication Index score (CCI).¹²⁵ Data will be collected as a continuous variable and calculated through the sum of morbidity and mortality presented on the Clavien Dindo classification.¹²⁶ CCI score will be calculated at the 30 day follow up.

CCI will be described as mean plus standard deviation (SD). However since we expect CCI to be right skewed (i.e. tail to the right) we will also describe CCI as median plus interquartile range (IQR) and percentage above 20.

We will visually check the distribution of the CCI data using histograms and calculating skewness and kurtosis. If necessary and if possible the data will be normalized by applying (normal) logarithmic transformation.

To test the hypothesis (H0) that the study arms result in similar CCI's (i.e. prehabilitation does not prevent postoperative complications), we will use the student T-test if data follow a normal distribution, a Mann-Whitney U if data do not follow a normal distribution or statistical methods that take into account a possible zero-inflated nature of the data.

The second primary/confirmatory outcome is the patients' functional capacity, as measured by the six-minute walk test (6MWT). The 6MWT is a continuous variable and calculated at baseline (inclusion to the study), a few days before surgery and 4 and 8 weeks after surgery.

Data will be described by means plus SD per time point. To accommodate the repeated measurements within individuals we will use a generalized linear mixed model to statistically test the hypothesis of both study arms being equal regarding functional capacity over time.

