4.4 Sample size calculation

The sample size calculation is based on the primary aim, to lower postoperative complications as determined according to the CCI score. With our population variables, CCI mean is 10.4 (SD 14), aiming to see decrease of 30%. We use an alpha of 0.05 and power of 0.80 (two-sided test). 10% dropouts are expected. We than need 708 patients, 354 per arm. This gives us a 100% efficacy to see a 6MWT proportion of improvement difference (55% versus 20%) as observed in previous studies.^{7,8} Each year around 800 eligible CRC patients undergo surgery in the participating hospitals in total, indicating that we will finish inclusion within 2 year time, with subsequent follow-up of 1 year.

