5. TREATMENT OF SUBJECTS

5.1 Investigational product/treatment

1. Patient triage medical conditions

Patient triage will allow us to tailor perioperative management, which may lower the risk for postoperative complications 30% in 'the risky' group. An anaerobic threshold (AT) value of the VO₂max test of 10 ml/kg/min gives 0.88 specificity and 0.79 sensitivity with area under curve of 0,85 for risk of complications.⁵³ Also severe pulmonary and cardiac disease will often be detected and scaled upon severity with exercise testing.

Triage will also focus on anemia, to identify patients' cardiopulmonary comorbidity using VO₂ peak tests. Patients will be screened preoperatively (4 weeks before surgery) to capture insufficient hemoglobin levels (thresholds in Canada: >11.2 g/dl, Europe: >7mmol/l). In case of iron insufficiency, hemoglobin levels will be optimized using iron injections. In combination with training it may give substantial effect.

Triage described above will be applied to the intervention group as well as controls.

2. Prehabilitation intervention

The intervention described below will only be given to the intervention arm of this study. The only exception is the smoke-cessation program, which will be offered to all patients.

Exercise program

An exercise specialist (kinesiologist, sport physician) will assess patients' mobility and capacity to undertake exercise. All participants will undergo a cardiopulmonary exercise test (CPET) and the exercise intensity will be defined and personalized on the individual CPET values. Based on the evaluation, a personalized program from the standardized program will be coordinated, as defined in appendix II. Additional to the preoperative exercise program, patients will receive information regarding breathing techniques to prevent occurrence of pneumonia.

With the intervention we try to achieve a maximum training stimulus in combination with a recovery diet, in order to achieve these goals in 4 weeks.

The program exists of several components:

- Strength training and high intensity interval training: this will be done 3 times a week supervised in the hospital. The strength training consists of 2 series of 10 repetitions of 6 exercises targeting all major muscle groups. The high intensity interval training aimed at 90% of the VO₂-peak
- Homework endurance training (low to moderate intensity): 4 times a week done at home.

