13. APPENDICES

Appendix I

Table 1. Prehabilitation randomized controlled trial scheme

Weeks	Preoperative			Operation	Postoperative		
	-5 Before start	-4 Baseline	-1 Preoperative	0 Surgery	4 30 day follow up	8 8 weeks follow up	52 1 year follow up
Gastroenterologist	Inform patient	-	-	-	-	-	-
Sport physician	-	Informed consent VO2max Anaerobic threshold Exercise-ECG	VO2max Anaerobic threshold Exercise-ECG	-	VO2max Anaerobic threshold Exercise-ECG	-	-
Physiotherapist	-	6MWT Stair climb test Sit-to-stand test 1-RM test Activity questionnaire (derived from CHAMPS)	6MWT Stair climb test Sit-to-stand test 1-RM test Activity questionnaire	-	6MWT Stair climb test Sit-to-stand test 1-RM test Activity questionnaire	6MWT Stair climb test Sit-to-stand test 1-RM test Activity questionnaire	-
Dietician		Food diary (3 days) Height, weight Weight loss %* Wrist/abdominal/ Upper arm circumference Skinfold measurements Hand grip strength PG-SGA	Food diary (3 days) Height, weight Weight loss %* Wrist/abdominal/ Upper arm circumference Skinfold measurements Hand grip strength PG-SGA	-			-
Psychologist	-	Intake when indicated (details in protocol)	-	-	-	-	-
Anesthesiologist	-	-	Preoperative screening**	ERAS**	-	-	-
Surgeon	-	-	ERAS**	-	-	-	-
Surgical resident	-	-	-	-	Outpatient data	-	-
Researcher/ Case manager	Inclusion patient	Intake Coping with anxiety HRQoL GAD-7 PHQ-9 Fried Frailty Score G8 score	HRQoL GAD-7 PHQ-9 Program evaluation & health costs (brief)	-	Weight and weight loss %* Hand grip strength PG-SGA score 30-day morbidity and mortality HRQoL GAD-7 PHQ-9 Program evaluation Health costs	Weight and weight loss %* Hand grip strength PG-SGA HRQoL GAD7 PHQ-9	Mortality Activity questionnaire Health and life style HRQoL GAD-7 PHQ-9

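### The primary CCI test uses no baseline covariate, although anaerobic threshold is scheduled at baseline in both arms and the protocol rates it as prognostic: a missed gain in power, not a sample-size error

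*Protocol*

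**What the plan says.** Section 9.6 sets out how CCI is compared between arms: "we will use the student T-test if data follow a normal distribution, a Mann-Whitney U if data do not follow a normal distribution". The sentence then allows a third route, methods suited to possibly zero-inflated data, without naming one. The same section expects CCI to be right-skewed. It names no baseline covariate for any of the three routes.

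Section 5.1, under patient triage, rates AT as a predictor: "An anaerobic threshold (AT) value of the VO₂max test of 10 ml/kg/min gives 0.88 specificity and 0.79 sensitivity with area under curve of 0,85". The outcome it refers to is risk of complications. The triage applies to both arms.

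Appendix I, Table 1 lists "Informed consent VO2max Anaerobic threshold Exercise-ECG" for the sport physician at week -4, and section 3 states that the appendix measurements apply to both arms. Under section 10.2 the patient learns the allocation only after the baseline measurements, so AT is a pre-treatment measure.

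Section 4.4 sizes the trial on a difference in mean CCI: "With our population variables, CCI mean is 10.4 (SD 14), aiming to see decrease of 30" per cent, two-sided alpha 0.05, power 0.80. It adds "10% dropouts are expected" and concludes "We than need 708 patients, 354 per arm".

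The opening of the statistical analysis section announces a detailed statistical analysis plan, to be available before the final data freeze. That plan was not at hand.

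**The concern.** CCI drives the sample size, and the trial has no more than its nominal 80% power for the targeted reduction. CCI has no baseline value of its own, so any gain in precision has to come from another prognostic measure. AT is the one for which the protocol gives a figure, and it is to be collected before treatment in both arms. Leaving it out keeps the residual variance higher than necessary. It also leaves the primary estimate unadjusted for chance imbalance in fitness, which is what the intervention targets.

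Timing matters as well. Section 9.9 plans a comparison of CCI halfway through, with stopping and sample-size recalculation attached. A covariate first named after that comparison could be suspected of having been chosen on the data.

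**Working it through.** **Inputs from section 4.4.** Control mean CCI 10.4, SD 14, reduction 30%, so the difference is 0.30 × 10.4 = 3.12. Two-sided alpha 0.05, power 0.80, dropout 10%.

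**The plan's own figure.** The two-sample t-test formula gives 317.03, hence 318 per arm. 318/0.90 = 353.3, hence 354 per arm and 708 in total, which is the protocol's number. (The normal approximation gives 317 per arm and 706 in total.)

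**Unadjusted power at 318 per arm.** 3.12 / (14 × √(2/318)) = 2.81, and Φ(2.81 − 1.96) = 80.2%.

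**From an AUC to a share of CCI variance.** The documents give no correlation between AT and CCI, so assumptions are needed. AT is taken as normal with equal variance in patients with and without complications, and as unrelated to severity among those with complications. With p the proportion with any complication:

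- Separation: d = √2 × Φ⁻¹(AUC). For AUC 0.85, d = 1.466.
- Variance of any versus no complication explained by AT: d² / (d² + 1/(p(1−p))).
- Share of CCI variance due to any versus no complication: p(1−p)(10.4/p)² / 14².
- R² for CCI is the product of the last two.
- Adjusted power: Φ(2.81/√(1−R²) − 1.96).

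Sections 1 and the Summary put complications at up to 50%. The value 40% is an assumption, used to show the range.

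| AUC | p = 0.50: R², power | p = 0.40: R², power |
|---|---|---|
| 0.70 | 0.067, 82.9% | 0.097, 84.0% |
| 0.75 | 0.102, 84.3% | 0.148, 86.1% |
| 0.85 | 0.193, 87.9% | 0.282, 91.2% |

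Worked example for AUC 0.85 and p = 0.50: 0.349 × 0.552 = 0.193, and Φ(2.81/√0.807 − 1.96) = 87.9%.

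**Check on the data shape that section 9.6 expects.** CCI was simulated as zero-inflated gamma, matched to mean 10.4 and SD 14, with 318 per arm and 4,000 runs per setting. The proportion with complications was 38% or 50%, the AUC 0.70 or 0.85, and the 30% reduction acted either on incidence or on severity.

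- Linear model with AT against the t-test: a gain of about 2 to 8 points. The smallest was 90.1% to 92.0%; the largest was 83.0% to 91.4%.
- Rank-based ANCOVA against Mann-Whitney: a gain of about 1 to 16 points. The smallest was 95.7% to 96.8%; the largest was 66.5% to 82.3%.
- Across families the order changes. For an incidence effect with 50% complications, unadjusted Mann-Whitney had 95-96% power against 86-90% for the adjusted linear model. For a severity effect, Mann-Whitney fell to 40-66% while the adjusted linear model had 92-97%.

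In a separate simulation of 1,500 runs per setting, the type I error of the linear model with robust standard errors was 4.7% to 5.8%, consistent with 5%.

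**The case against.** **Nothing in section 9.6 is invalid.** An unadjusted randomised comparison holds its type I error, which already allows for chance imbalance. The 708 reproduces exactly and 80% power is met. This stands, and it is why the point concerns efficiency only. A reader might infer that the trial is underpowered or the test biased; the documents support neither.

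**Covariates belong in the statistical analysis plan, and a zero-inflated model could carry them.** This stands in part: the third route is open, and the separate plan may add adjustment. But section 9.6 is not silent. It commits to two tests that cannot take a covariate, and the separate plan is promised only before the final data freeze, which may come after the interim look at CCI.

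**The AUC may not transfer.** It comes from a cited study, concerns any complication rather than the CCI score, and several features of this protocol could weaken it. AT-guided triage alters care in both arms (5.1). The exclusions in 4.3 narrow the range of fitness. The intervention aims to raise VO₂-peak at AT by 15% (5.1), so baseline AT may predict less in that arm. All of this stands, which is why the lower AUC values belong in the range.

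**A loss of 8 to 13 points is a tempting summary, but it is not supported.** The upper end needs 36% of patients with complications, which gives 92.8%. The minimum compatible with mean 10.4 and SD 14 is 10.4²/(10.4² + 14²) = 35.6%. At 36%, patients with complications would have CCI of mean 28.9 and SD only 3.2, which is implausible for a graded severity index. The lower end already assumes that 0.85 transfers.

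**Conclusion.** The point holds as a missed gain. The documents state a primary test that cannot use a baseline measure they schedule in both arms and themselves describe as prognostic. From 80.2%, power would rise by about 3 to 6 points if the AUC here is 0.70-0.75, and by about 8 to 11 points only if 0.85 applies to this population and to CCI. These figures assume 40-50% of patients with complications, a constant SD of 14, and AT unrelated to severity once a complication occurs. They describe the t-test route. For skewed or zero-inflated data the gain within each test family was positive in every simulated setting but varied widely.

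Two further inferences should be avoided. AT is scheduled for every patient, which does not mean that every patient will have a usable value. Nor does the case for a covariate show that a linear model for mean CCI should replace the other routes, since which family has more power depends on whether prehabilitation acts on the incidence or the severity of complications.

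**What to change.** In section 9.6, prespecify baseline AT, as a continuous variable, as a covariate in whichever CCI analysis is used, and do so before the interim analysis:

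- in place of the t-test, a linear model with arm and AT and robust standard errors;
- in place of Mann-Whitney U, a rank-based ANCOVA or a proportional-odds model with arm and AT;
- in a zero-inflated model, AT as a covariate.

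Where AT cannot be determined, use mean imputation with a missing indicator, so that no randomised patient is dropped. Keep the unadjusted test as a sensitivity analysis.

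Use the same model for the interim test and sample-size recalculation in section 9.9. Required size scales with 1−R², so recalculating on the unadjusted variance would overstate it by the share that AT explains (R² of about 7% to 28% in the table) and bear on the 1000-patient limit.

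The cost is a change of wording in 9.6 and 9.9, with no new data and no extra patients. The downsides are small: AT may be undeterminable in some patients, and the gain is slight if AT proves weakly prognostic here.

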2. OBJECTIVES

Primary Objective: To investigate if multimodal prehabilitation could decrease postoperative complications and improve functional capacity pre- and postoperatively for patients undergoing colorectal surgery for cancer.

Secondary Objective(s): To investigate the effects of multimodal prehabilitation on Health Related Quality of Life, nutritional status, length of hospital stay and cost-effectiveness.

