8. METHODS

8.1 Study parameters/endpoints

8.1.1 Main study parameter/endpoint

The first primary outcome is postoperative complications as measured by the Comprehensive Complication Index score, a combined outcome measure of morbidity and mortality.⁷⁸

The second primary/confirmatory outcome is the patients' functional capacity 8 weeks postoperatively, as measured by the six-minute walk test (6MWT).

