9.9 Interim analysis (if applicable)

Due to limited clinical data and resulting uncertainty regarding effect size of the primary endpoint – CCI - an interim analysis will be performed. The interim analysis is planned if half of the intended number of subjects have completed the 8 week assessment (i.e. timing of the primary endpoint assessment). The intention of the interim analysis is to terminate the study if there is a statistical significant difference between study arms at an alpha of 0.0054 (O'Brien-Fleming stopping rule) or if the recalculated sample size is deemed unattainable (i.e. larger than 1000 patients) or if the difference is not clinically relevant (<5 percent)

The sample size at the time of interim analysis will be sufficient to still show clinically relevant statistical differences regarding the second primary endpoint (i.e. 6MWT).

The interim analysis will be performed by the epidemiologist of the MMC, who is not a member of the DSMB. Early termination of the study will be decided upon by the DSMB.

To account for the alpha spending upon interim analysis (the final alpha will be 0.049), the sample size needs a minor adjustment from 708 to 713 patients. If the sample size recalculation in the interim analysis implies adjustment of the required sample size, this will be processed through an amendment to the protocol.

10. ETHICAL CONSIDERATIONS**10.1 Regulation statement**

The study will be conducted according to the principles of the Declaration of Helsinki⁵⁵ and in accordance with the Medical Research Involving Human Subjects Act (WMO).

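### The second primary endpoint is the 6MWT at 8 weeks after surgery, but the planned test compares the arms over four visits, so a gain confined to the preoperative visit can make it significant

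*Protocol*

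**What the plan says.** Section 8.1.1 defines the second primary/confirmatory outcome as "functional capacity 8 weeks postoperatively, as measured by the six-minute walk test (6MWT"). Section 9.9 also ties the primary endpoint to that visit: the interim analysis waits until half of the patients have "completed the 8 week assessment (i.e. timing of the primary endpoint assessment"). The complication index is scored at 30 days, so the visit named there fits only the 6MWT.

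Section 9.6 restates the outcome without a visit. The 6MWT is "calculated at baseline (inclusion to the study), a few days before surgery and 4 and 8 weeks after surgery", and a generalized linear mixed model is to "statistically test the hypothesis of both study arms being equal regarding functional capacity over time".

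Section 4.4 sizes the trial on the complication index and adds that the number gives full power for a "6MWT proportion of improvement difference (55% versus 20"%). It names no visit for this proportion, and Section 9.6 treats the 6MWT only as a continuous variable.

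The primary objective in Section 2 is broader than Section 8.1.1: to "decrease postoperative complications and improve functional capacity pre- and postoperatively".

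**The concern.** Equality at 8 weeks and equality over time are different null hypotheses. The second is false whenever the arms differ at any visit after randomisation, including the visit before surgery.

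In this trial a preoperative difference is the expected result. Only one arm trains for four weeks, and the 6MWT is repeated directly afterwards. Section 5.1 aims for a 10% increase in distance in patients walking less than 500 m, which is 40 m for a patient who walks 400 m. Whether any of that gain survives surgery to 8 weeks is the question in Section 8.1.1, and the stated test cannot isolate it.

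At stake is the meaning of a significant result on a primary endpoint. It could be reported as better recovery at 8 weeks when the arms are the same at 8 weeks and differed only before the operation.

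**Working it through.** **The plan's own figures.** Section 4.4 gives "CCI mean is 10.4 (SD 14), aiming to see decrease of 30"%, a difference of 0.30 × 10.4 = 3.12, and states "We use an alpha of 0.05 and power of 0.80 (two-sided test"). The normal approximation 2 × 14² × (1.960 + 0.842)² / 3.12² gives 316.1, so 317 per arm. With the t distribution it is 318. Allowing for 10% dropout, 318 / 0.9 = 353.3, so 354 per arm and 708 in total, as stated. For 55% v 20%, z = 0.35 / √[(0.55 × 0.45 + 0.20 × 0.80) / 318] = 9.8, so the claim of full power also holds for that measure.

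**Assumptions for the check.** There are n = 318 per arm with complete data, and alpha is 0.05 two-sided. Outcomes are in SD units. The true arm difference over the four visits is (0, 0.2, 0, 0). Within-patient correlation ρ is 0.6, 0.7 or 0.8, with compound symmetry or AR(1). The protocol gives no 6MWT SD and no between-visit correlation. Section 8.3 gives only a test-retest reliability of 0.73 to 0.99 and a 20 m threshold for true change. If the SD were 100 m, 0.2 SD would be that 20 m.

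Section 9.6 does not say which model term carries the test, so three readings are worked through. Formulas are for compound symmetry; √(n/2) = √159 = 12.61.

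1. *Plain arm effect, equal weight on four visits.* Mean difference 0.05; z = 0.05 × 12.61 / √[(1 + 3ρ)/4]. For ρ = 0.6, 0.7, 0.8, z = 0.75, 0.72, 0.68.
2. *Baseline-adjusted average of the three later visits.* Mean difference 0.0667; z = 0.0667 × 12.61 / √[(1 + 2ρ)/3 − ρ²]. This gives z = 1.38, 1.51, 1.77.
3. *Arm-by-visit test, 3 df.* Noncentrality λ = 159 × 0.2² × (3/4) / (1 − ρ) = 4.77 / (1 − ρ), so 11.9, 15.9, 23.9, against a critical value of 7.81.
4. *8-week contrast.* The true difference is zero, so it rejects at 5% whatever the correlation.

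Chance of a significant result when the 8-week difference is zero:

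| Reading | Compound symmetry, ρ = 0.6 / 0.7 / 0.8 | AR(1), ρ = 0.6 / 0.7 / 0.8 |
|---|---|---|
| Plain arm effect, four visits | 12 / 11 / 11% | 13 / 12 / 11% |
| Baseline-adjusted average | 28 / 33 / 42% | 21 / 22 / 26% |
| Arm-by-visit, 3 df | 84 / 93 / 99% | 88 / 96 / >99% |
| 8-week contrast | 5% | 5% |

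The plain arm effect here weights visits equally. A fit that weights by precision under AR(1) gives each middle visit the weight (1 − ρ)/(4 − 2ρ), with variance factor (1 + ρ)/(4 − 2ρ). At ρ = 0.7, z = 0.2 × 0.115 × 12.61 / √0.654 = 0.36, a rate of about 6.5%. That is smaller, but still above 5%.

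**In metres.** A gain of 20 m before surgery only, with SD 80 to 120 m and correlation 0.60 to 0.85, gives 9–18%, 16–70% and 67% to over 99% for the three readings in the same order.

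**The case against.** The best defence is that a test over time fits the trial's aim. Section 2 puts functional capacity both before and after surgery in the primary objective. Section 8.3 measures the 6MWT at four visits to follow the whole perioperative period, and the Summary names no visit. A preoperative gain is then part of what the trial set out to show. This stands in part: a reader might infer that such a gain is merely a false route to significance, and Section 2 does not support that. But the defence moves the conflict to Section 8.1.1, which does fix 8 weeks. The two still need reconciling.

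A second defence is that model terms belong in the SAP announced ahead of Section 9.6. For the terms, yes. But the protocol itself states both an endpoint and a hypothesis, and they differ, so an SAP faithful to one departs from the other. Section 9.7 does provide single-visit tests for secondary outcomes; the confirmatory 6MWT outcome has none.

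Third, Section 9.6 also asks for means and SDs at each time point, so a null result at 8 weeks would be visible. That helps the reader but does not change what the test tests.

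Three further inferences go beyond the documents:

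- *That a preoperative gain would almost always produce significance.* The 84% to over 99% belongs to the arm-by-visit reading alone, and Section 9.6 specifies no such term.
- *That baseline is wrongly analysed as an outcome, at a cost in precision.* Section 9.6 lists baseline as a measurement and does not fix its role. At ρ = 0.7 the variance factors are 1 − ρ² = 0.51 with baseline adjustment, 1 for raw values and 2(1 − ρ) = 0.60 for change scores, reductions of 49% and 15%. Neither raw values nor change scores are the planned analysis, so these are not losses of the plan.
- *That the trial is wrongly sized.* The 708 comes from the complication index and reproduces. The 55% v 20% remark is an addition that describes a different measure.

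**Conclusion.** The point holds. As written, the confirmatory test of the second primary outcome does not test the outcome that Section 8.1.1 defines, and the 6MWT power statement belongs to a third quantity that is never analysed.

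The direction does not depend on how the sentence is read: every reading exceeds 5% for the 8-week claim. The size does, running from about 11–13% through 21–42% to 84% or more for a preoperative-only difference of 0.2 SD. These figures rest on an assumed effect pattern, correlation and complete data; the protocol supplies none of them. The mismatch in the text needs no assumption.

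**What to change.** In Section 9.6, name the between-arm difference in 6MWT metres at 8 weeks as the confirmatory test. Estimate it from the planned mixed model with arm, visit and arm-by-visit terms, adjusted for baseline 6MWT either as a covariate or by constraining the arms to be equal at baseline. Present the preoperative and 4-week contrasts as supportive.

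If the preoperative effect is meant to count, amend Section 8.1.1 instead so that the endpoint covers it. State there that a significant result does not by itself show a difference at 8 weeks.

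In Section 4.4, label the 55% v 20% statement as supportive, or replace it with power for the 8-week mean difference. As an illustration, for an assumed 0.2 SD with 318 per arm under compound symmetry, z = 0.2 × 12.61 / √(1 − ρ²), which gives about 88% to 99% power for ρ from 0.6 to 0.8. Under AR(1) the baseline-to-8-week correlation falls to ρ³ and the range is about 73% to 84%.

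The cost is a few sentences in a protocol amendment, made before the data are analysed. The visits, data, model family and sample size stay as they are.
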